## 10.2 Pooling of small centers

Primary efficacy analysis will be performed on the FAS Sample which comprises those subjects in the Randomized Sample who have baseline and at least 1 postbaseline assessment of MADRS total score. Small centers will be defined as centers that do not have at least one evaluable subject (evaluable with regard to the primary efficacy variable) in each treatment arm. All small centers will be pooled to form "pseudo centers"

#### 10.3 Scales: Rules for Scoring and Handling of Missing Data

## 10.3.1 Montgomery-Asberg Depression Rating Scale (MADRS)

The MADRS is utilized as the primary efficacy assessment of a subject's level of depression. The MADRS consists of 10 items, all rated on a 0 to 6 scale with zero being the "best" rating and 6 being the "worst" rating. The MADRS total Score is the sum of ratings for all 10 items; therefore, possible total scores range from 0 to 60. The MADRS total score will be unevaluable if less than 8 of the 10 items are recorded. If 8 or 9 of the 10 items are recorded, the MADRS total Score will be the mean of the recorded items multiplied by 10 and then rounded to the first decimal place. MADRS is assessed at each scheduled visit.

#### 10.3.2 Generalized Anxiety Disorder-7 (GAD-7)

The GAD-7 is a self-reported questionnaire designed to assess anxiety in subjects. The scale contains 7 items and each item is rated from 0 (not at all) to 3 (nearly every day). The total score ranges from 0 to 21. A higher score on the GAD-7 represents greater anxiety symptomatology. GAD-7 is assessed at each scheduled visit.

# 10.3.3 Clinical Global Impression Severity of Illness Scale (CGI-S)

The severity of agitation for each subject will be rated using the Clinical Global Impression-Severity of Illness Scale (CGI-S). To perform this assessment, the investigator (or designee) will answer the following question: "Considering your total clinical experience with this particular population, how mentally ill (as related to agitation) is the subject at this time?" Response choices are 0 = not assessed; 1 = normal, not at all ill; 2 = borderline mentally ill; 3 = mildly ill; 4 = moderately ill; 5 = markedly ill; 6 = severely ill; and 7 = among the most extremely ill subjects. The score 0 (not assessed) will be set to missing. The CGI-S is therefore a 7-point scale from 1 through 7. CGI-S is assessed at each scheduled visit in the treatment period.

## 10.3.4 Patient Health Questinaire-9 (PHQ-9)

The PHQ-9 is a standardized, self-administered rating scale that assesses the severity of depressive symptoms. The scale consists of 9 items, representing the 9 criteria upon which the diagnosis of DSM-IV depressive disorders is based. Each item is rated from 0 (not at all) to 3 (nearly every day). The total score ranges from 0 to 27. A higher score on the PHQ-9 represents a higher severity of depressive symptoms. PHQ-9 is assessed at screening, and Weeks 4 and 6.

[figure not shown]
# 10.3.5 World Health Organization Disability Assessment Schedule 2.0 (WHODAS 2.0)

The WHODAS 2.0 is a 36-item self-assessment scale to measure a subject's function and disability across 6 domains of life: cognition (understanding and communicating), mobility (moving and getting around), self-care (hygiene, dressing, eating, staying alone), getting along (interacting with others), life activities (domestic responsibilities, leisure, work and school), and participation (community and society). Each item is rated from 0 (none) to 4 (extreme or cannot do). The total score of the 36 items will be converted into a metric ranging from 0 (no-disability) to 100 (full- disability) by dividing the total score by the maximum possible value of the total score, which is 144 for 36 items and 128 for 32 items if items D5.5-D5.8 were skipped, and multiplying by 100. In situation where one or two items are missing, it will be handled as described in the manual of WHODAS 2.0^14, the mean score across all items within the domain should be assigned to the missing items. This method should not be used if more than two items are missing. In addition, if domain-wise scores are being computed for domains, the two missing items should not come from the same domain. WHODAS 2.0 is assessed at the baseline and Week 6.

# 10.3.9 Columbia-Suicide Severity Rating Scale (C-SSRS)

Suicidality will be monitored during the trial using the C-SSRS. This trial will use the "baseline/screening" and "Since Last Visit" versions of the scale. The "Baseline/Screening" Version will be used for the first administration (at the screening visit). This version will evaluate a lifetime assessment of suicidal ideations and behaviors, as well a past 12-month evaluation of suicidal ideations and a past 24-month evaluation of suicidal behaviors. Subsequent visits will utilize the "Since Last Visit" Version.

#### 1 Introduction

This addendum to the statistical analysis plan (SAP) version 1.0 is to:

- Remove the key secondary efficacy endpoint and corresponding multiplicity adjustment rule.
- Specify the efficacy endpoints for supportive analyses for the primary efficacy endpoint and for the durability of the effect.
- Modify the criteria for defining Per-protocol (PP) Analysis Sample.

After the approval of the original SAP (version 1.0, issued on February 13, 2022). The addition and changes will have no impact on the overall type-I error rate. The statistical methodology, data analysis algorithms, and conventions remain the same as those in the original SAP, unless being specified below.

## 2 Removing Key Secondary Efficacy Endpoint

The change from baseline to Week 6 in GAD-7 total score, mentioned in Section 8.2 in the original SAP, will be considered as a secondary efficacy endpoint rather than the key secondary efficacy endpoint in this study. The hierarchical testing approach used to control the overall type-I error rate on the primary efficacy endpoint and the key secondary efficacy endpoint will no longer be applicable.

To control the overall type I error for the primary efficacy endpoint, it will be tested at a significance level of 0.049 (2-sided) as planned. All rest efficacy endpoints, including secondary efficacy, other efficacy, and CCI , will be tested at a nominal 0.05 level (2-sided) individually without adjusting for multiplicity.

# 3 Supportive Analyses for the Primary Efficacy Endpoint

The following endpoints from Section 8.3 (Other Efficacy Endpoints) CCl

in the original SAP will be served as supporting evidence to the primary efficacy endpoint:

- 1) Change from baseline to Weeks 2 and 4 in the MADRS total score
- 2) MADRS full response at Weeks 2, 4, and 6
- 3) MADRS partial response at Weeks 2, 4, and 6
- 4) MADRS remission at Weeks 2, 4, and 6

Confidential - Proprietary Information

SAP 345-201-00002

Note that in order to differentiate with MADRS partial response, MADRS response in the original SAP is renamed as MADRS full response.

# 4 Supportive Analyses for Assessment for Durability Based on MADRS Total Score

The following endpoints from Section 8.3 (Other Efficacy Endpoints) CC in the original SAP will be served as supporting evidence to the durability of effect assessed based on MADRS total score. They will be analyzed by the same statistical model as used for Endpoints (2) - (4) in Section 3 of this addendum.

- 1) MADRS full response at Weeks 8 and 10
- 2) MADRS partial response at Weeks 8 and 10
- 3) MADRS remission at Weeks 8 and 10

# 5 Modification on PP Analysis Sample

[figure not shown]
The criteria 3 and 4 in Section 5.1 in the original SAP will not be used for defining PP Analysis Sample.

[figure not shown]
The PP Analysis Sample will only be used for sensitivity analysis for the primary efficacy variable and the secondary efficacy variable.

[figure not shown]

[figure not shown]
Confidential - Proprietary Information

[figure not shown]
16 Nov 2022

[figure not shown]

[figure not shown]

# **List of Abbreviations and Definitions of Terms**

Abbreviation	Definition
ADT	Antidepressant therapy
AE	Adverse event
ANCOVA	Analysis of Covariance
DMC	Data Monitoring Committee
DSM-5	Diagnostic and Statistical Manual of Mental Disorders, Fifth
	Edition
EFMT	Emotional Faces Memory Task
FAS	Full analysis set
GAD-7	Generalized Anxiety Disorder-7
IA	Interim analysis
IAP	Interim analysis plan
IDAG	Independent Data Analysis Group
IVRS	Interactive voice response system
IWRS	Interactive web response system
LOE	Lack of efficacy
LS	Least square
MADRS	Montgomery-Asberg Depression Rating Scale
MAR	Missing at random
MCAR	Missing completely at random
MDD	Major depression disorder
MI	Multiple imputation
MMRM	Mixed-effect model repeated measure
MNAR	Missing not at random
OC	Observed-case
OPDC	Otsuka Pharmaceutical Development & Commercialization, Inc.
PMM	Pattern mixture models
SAP	Statistical analysis plan
SMT	Shapes Memory Task
SMS	Short message service
UN	Unstructured

#### 1 Introduction

This interim analysis plan (IAP) documents the statistical methodology, data analysis algorithms, and conventions to be applied in the interim analysis (IA) and reporting of efficacy data of Trial 345-201-00002.

The primary objective is to compare the effectiveness of CT-152 with sham, in adult subjects diagnosed with major depression disorder (MDD) who are on antidepressant therapy (ADT) monotherapy.

The safety objective is to evaluate the safety of CT-152 in adult subjects diagnosed with MDD who are on ADT monotherapy.

This is a multi-center, randomized, controlled trial to evaluate the effectiveness of CT-152 in adult subjects diagnosed with MDD who are on ADT monotherapy for the treatment of depression. The trial population will include male or female subjects aged 22 to 64 years old at the time of informed consent, with a current primary diagnosis of MDD based on the criteria in the *Diagnostic and Statistical Manual of Mental Disorders*, Fifth Edition (*DSM-5*), single or recurrent episode, without psychotic features and do not meet criteria for MDD with mixed features subtype, and who are on ADT monotherapy.

Subjects will participate in the trial for up to 13 weeks. The trial will include a screening period of up to 3 weeks, a treatment period for 6 weeks, and an extension period for 4 weeks. Eligible subjects will be randomized to 1 of 2 digital mobile applications (CT-152 or sham) on Day 1. During the treatment period (Day 1 [baseline] to Week 6), subjects will have a remote visit at Weeks 2, 4, and 6 and will be contacted by telephone at Weeks 1, 3, and 5. Subjects will be expected to be adherent with the recommended schedule of their digital mobile application exercises during the treatment period. After Week 6, subjects will continue participation in the trial during the extension period (Weeks 7 to 10). In the extension period, the digital mobile applications will remain installed for each group, with the Emotional Faces Memory Task (EFMT) and Shapes Memory Task (SMT) no longer available. Psychotherapy content provided previously will remain available for optional reference in the CT-152 group but no new therapeutic content will be introduced and no required treatment schedule is in place. The 2 groups will each receive brief short message service (SMS) messages in the extension period reminding subjects of the previously completed CT-152 or sham treatment courses, and will continue their ADT. Subjects will have a remote visit at Weeks 8 and 10 and will be contacted by telephone at Weeks 7 and 9. The end of the trial will be Week 10.

#### 2 Statistical Methods

## 2.1 Sample Size and Power Justification

The primary efficacy endpoint is the change from baseline at Week 6 in Montgomery-Asberg Depression Rating Scale (MADRS) total Score. The trial will compare CT-152 to Sham, randomized at a ratio of 1:1, with an overall alpha of 0.05 for the primary efficacy endpoint.

In this trial, we plan to detect a 3-point difference on the primary efficacy endpoint between the treatment groups. The 3-point treatment difference is above the range. Therefore, the initial sample size is calculated to detect a 3-point difference between CT-152+ADT and Sham+ADT in the change from baseline in MADRS total score with 85% power at a 2-sided  $\alpha = 0.05$  level, assuming a common standard deviation of 9. The resulting sample size is 324 evaluable subjects in total (162 subjects in each arm). To compensate for subjects that fail to have evaluable assessments of MADRS total score in the full analysis set (FAS) Sample (estimated at up to 10% of all subjects), a total of 360 subjects (180 subjects in each arm) will be randomized in this trial.

Due to the limitations of applying assumptions on the treatment effect size, and in order to ensure adequate power of the trial, an unblinded IA will be conducted by a Data Monitoring Committee (DMC) on approximately the first 180 randomized subjects who have either completed the Week 6 visit or discontinued prior to Week 6. The final sample size could be increased to 540 subjects (270 subjects in each arm) as per recommendation of the DMC. Using the O'Brien-Fleming boundaries, an alpha level of 0.003 (2-sided) is allocated to this interim analysis. The alpha level left for the final analysis is 0.049 (2-sided). The power and sample size were obtained using the PASS 14 (2015) statistical computing software.

#### 2.2 Interim Efficacy Analysis

The interim analysis of efficacy data will be performed by an Independent Data Analysis Group (IDAG), the Labcorp DMC Support Team, in coordination with DMC. Reference is made to the DMC charter for details of its roles and responsibilities. The purpose of the interim analyses is to decide whether there is sufficient evidence that the study will be stopped to declare efficacy or futility, or additional subjects are needed to have sufficient power to achieve the primary objective. To this end, the primary efficacy endpoint of change from the baseline to Week 6 in MARDS total score and the durability of effect of

6

Confidential - Proprietary Information

CT-152 based on MADRS total score will be analyzed. The analysis for the key secondary efficacy endpoint of the change from the baseline to Week 6 in Generalized Anxiety Disorder-7 (GAD-7) total score and the durability of effect of CT-152 based on GAD-7 total score will also be provided.

The primary analysis will be performed on the FAS Sample which includes all randomized subjects who receive at least 1 occurrence of either CT-152 or sham use, and have both a baseline and at least one postbaseline assessment of MADRS total score. The primary efficacy analysis will be performed by fitting a mixed model repeated measurements (MMRM) analysis with an unstructured (UN) variance covariance structure, in which the change from baseline in MADRS total score (at Weeks 2, 4, and 6) during treatment period will be the dependent variable based on the OC data set. The model will include fixed class effect terms for treatment, visit, treatment by visit interaction, and site to assess heterogeneity of treatment effects. The model will also include an interaction term of visit by baseline MADRS total score as a covariate. The primary comparison between the CT-152+ADT and Sham +ADT at Week 6 will be estimated as the difference between Least Squares (LS) means utilizing the computing software SAS procedure PROC MIXED. In case there is a convergence problem with MMRM model with the unstructured (UN) variance covariance matrix, the following structures other than unstructured will be used in order of 1) heterogeneous toeplitz (TOEPH), 2) heterogeneous autoregressive of order 1 (ARH1), and 3) heterogeneous compound symmetry (CSH) and the first (co)variance structure converging to the best fit will be used as the primary analysis. If a structured covariance has to be used, the empirical "sandwich" estimator of the standard error of the fixed effects parameters will be used in order to deal with possible model misspecification of the covariance matrix.

To assess the durability of effect of CT-152, three MADRS assessments at Weeks 6, 8, and 10 will be included.

at Week 6 with statistical significance, durability will be demonstrated by a point estimate of the difference in change from baseline at Weeks 8 and 10 above 1.6, when comparing CT-152 and sham. Such point estimates will be provided using the same MMRM model in the primary efficacy analysis with change from baseline in MADRS total score at Week 8 and 10 as the dependent variable.

This key secondary efficacy endpoint will be analyzed by fitting the same MMRM model as described in the primary analysis with change from baseline in GAD-7 total score (at Weeks 2, 4, and 6) as the dependent variable.

Durability based on GAD-7 will also include 3 assessments, at Weeks 6, 8, and 10, demonstrating a numerically larger improvement on point estimate of the difference in

Confidential - Proprietary Information

7

change from baseline in GAD-7 total score at Weeks 8 and 10 in CT-152 compared to sham. Such point estimates will be provided using the same MMRM model in the key secondary efficacy analysis with change from baseline in GAD-7 total score at Week 8 and 10 as the dependent variable.

One unblinded IA for assessment of efficacy will be conducted on approximately the first 180 (50%) randomized subjects. This unblinded IA will be carried out when these subjects have either completed the Week 6 visit or discontinued prior to Week 6. The O'Brien-Fleming boundaries³ will be utilized in primary analysis for the rejection of the null hypothesis to maintain an overall nominal significance level of 0.05 (2-sided). The boundary values for the rejection of the null hypothesis are given in Table 2.2-1. Also, to control the overall type I error, the statistical tests based on the primary efficacy endpoint and the key secondary efficacy endpoint will be done using a hierarchical approach. The primary hypothesis will be tested at the 0.003 level at IA and if successful in rejecting the null hypothesis, analysis of the key secondary endpoint will be tested at the type I error level of 0.003. Similar rules will be carried out at the final analysis with the 0.049 level if the trial doesn't stop at IA. Should the primary outcome not achieve statistical significance, the key secondary endpoint will be categorized as other efficacy endpoint.

Table 2.2-1 Boundaries for Rejection of the Null Hypothesis for the Interim and Final Analyses

Analysis	Two-sided Alpha Level 
Interim analysis #1 (~ 50%)	0.003
Final analysis (100%)	0.049

<sup>1 Obtained using PASS 14(2015) sample size software.

The fraction of the sample size might not be consistent with the fraction of the information when the primary analysis is MMRM with high dropout rate. If there is a high dropout rate, the timing for the IA will use the rate of those subjects who complete the Week 6 assessment which would control the Type I error with the alpha spending function.

The IA results will be reviewed by the DMC. Should the interim analysis be performed at a different time, the Lan-DeMets Spending Function with O'Brien-Fleming boundary will be applied to adjust the critical values in order to guarantee an overall 0.05 alpha level.

With the interim data, the DMC will be allowed to make recommendations to stop the trial for efficacy, stop the trial for futility, or continue the trial with/without sample size adjustment, based on the p-value and the conditional power calculated on the primary efficacy endpoint. The details are listed Table 2.2-2. The sample size will be re-estimated

8

Confidential - Proprietary Information

only based on the conditional power determined at the interim analysis. The adaptive designs methodology published by Chen, DeMets, and Lan (2004) will be used to increase the sample size based on an interim estimate of the treatment effect size of the primary efficacy endpoint, possibly combined with other external information, without inflating the type I error.

Table 2.2-2 Interim Results and DMC Recommendation

Interim Results	Interim Analysis	Sample Size
	Recommendation	
p-value < 0.003 and all point estimates of difference in change from baseline to Week 6, 8, and	Stop for efficacy	N=180 (90/arm)
10 in MADRS total score are above 1.6.		
Conditional power  ≥ 85%	No adaption to the planned sample size	N=360 (180/arm)
50% < Conditional power  < 85%	Increase sample size up to 540	N=540 (270/arm)
15% < Conditional power¹ ≤50%	No adaption to the planned sample size	N=360 (180/arm)
Conditional power¹ ≤ 15%	Stop for futility	N=180 (90/arm)

<sup>1 The conditional power will be only based on the statistical test for the primary efficacy endpoint (ie, the change from baseline to Week 6 in MADRS total score).

If the study is terminated after claiming efficacy in the interim analysis, a "final" analysis will be performed. This "final" analysis will include the efficacy data occurring between the data cutoff for the interim analysis and the final database lock (i.e. all efficacy data up to database lock), and the alpha level for the "final" analysis will be derived based on the information fraction using the Lan-DeMets Spending Function with O'Brien-Fleming boundary. In order to make sure that the "final" analysis will be positive without doubt, criteria more conservative than the one provided in Table 2.2-1 are needed for making an efficacy claim at an interim analysis.

The sponsor will remain blinded to any modification of the primary model due to nonconvergence and should not be informed of any additional analysis or modification requested by the DMC and performed by unblinded statistician.

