## 8.1.1.2 Primary Analysis Method

The primary analysis will utilize a MMRM with an unstructured (UN) variance covariance matrix in which the change from baseline in MADRS total score at scheduled treatment period visits (Weeks 2, 4, and 6) will be the dependent variable based on the OC data set on FAS Sample. The model will include fixed class effect terms for treatment, visit, treatment by visit interaction, and site to assess heterogeneity of treatment effects. This model will also include an interaction term of visit by baseline MADRS total score as a covariate. The primary comparison between the CT-152+ADT or sham+ADT at Week 6 will be estimated as the difference between least squares means utilizing the computing software SAS procedure PROC MIXED.

The mathematical formula for the MMRM model is as follows:

$$\mathbf{y} = \mathbf{X}\boldsymbol{\beta} + Z\mathbf{u} + \epsilon$$

Where

y denotes the observed vector of change from baseline to Week 6 in MADRS total score;

X is the known matrix for the fixed effects and covariate;

 $\beta$  is an unknown fixed-effect parameter vector;

Z is the known matrix for the random effect of subject;

u is an unknown vector of random effect of subject with mean  $\mathbf{0}$  and variance-covariance matrix  $\mathbf{G}$  (unstructured covariance matrix);

 $\epsilon$  is an unknown vector of random errors with mean 0 and variance **R**.

In case there is a convergence problem with the MMRM model with the unstructured variance-covariance matrix, the following structures other than unstructured will be used in order of 1) heterogeneous toeplitz (TOEPH), 2) heterogeneous autoregressive of order 1 (ARH1), and 3) heterogeneous compound symmetry (CSH). The first (co)variance structure converging to the best fit will be used as the primary analysis. If a structured covariance has to be used, the "sandwich" estimator of the standard error of the fixed effects parameters will be used in order to deal with possible model misspecification of the covariance matrix.

Small trial sites will be defined as trial sites that do not have at least one evaluable subject (evaluable with regard to the primary efficacy variable) in each treatment arm. All small trial sites will be pooled to form "pseudo sites"

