#### 8.1.2 Technical Computation Details for Primary Efficacy Analysis

The SAS code for the PROC MIXED procedure to carry out the above MMRM analysis with an unstructured variance covariance structure is illustrated as follows:

```
proc mixed;
class treatment site visit subjid;
model change=treatment center visit treatment*visit baseline*visit /s cl
ddfm=kenwardroger;
repeated visit /type=un subject=subjid r rcorr;
lsmeans treatment*visit / pdiff cl alpha=0.05 slice=visit;
run;
```

where baseline is the last available measurement prior to the start of intervention with doubleblind digital therapeutic in the treatment period.

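### If the unstructured MMRM fails to converge, the fallback sandwich standard error has no named small-sample correction or degrees of freedom and, with one fixed effect per pooled site, comes out too small for the 0.003 and 0.049 tests

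*SAP*

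**What the plan says.** The primary model in Protocol 9.4.1.1.2, SAP 8.1.1.2 and IAP 2.2 is an MMRM on Weeks 2, 4 and 6 with unstructured covariance. Its terms are treatment, visit, treatment by visit, baseline by visit and site as a fixed class effect. There are about 50 sites. A site is pooled only when one arm has no evaluable subject there, so most sites keep their own parameter.

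On a convergence problem, heterogeneous Toeplitz, heterogeneous AR(1) and heterogeneous compound symmetry are tried in that order, and the result becomes the primary analysis. SAP 8.1.1.2 then states: "If a structured covariance has to be used, the 'sandwich' estimator of the standard error of the fixed effects parameters will be used". The Protocol has the same sentence. IAP 2.2 is more specific: "the empirical 'sandwich' estimator of the standard error of the fixed effects parameters will be used". The stated reason is protection against a misspecified covariance.

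A small-sample method appears only in the SAS code of SAP 8.1.2, which is for the unstructured model: "ddfm=kenwardroger". No text gives a correction or degrees of freedom for the fallback. The test levels do not depend on which standard error is used: "an alpha level of 0.003 (2-sided) is allocated to this interim analysis" and "The alpha level left for the final analysis is 0.049 (2-sided").

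**The concern.** An empirical sandwich estimates variance from raw residuals. Fitting many parameters shrinks those residuals, so the standard error is biased downward when fixed effects are numerous relative to subjects. At the interim there are about 162 evaluable subjects over about 50 sites, roughly three per site. The plan uses Kenward-Roger when the unstructured model converges, and names nothing comparable in the one branch that relies on a sandwich.

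If that branch runs, three things rest on a standard error that is too small: the p-value compared with 0.003, the conditional power behind the futility and sample-size zones (IAP Table 2.2-2 bases it on the same test), and the final comparison with 0.049. The plan commits to testing "with an overall alpha of 0.05 for the primary efficacy endpoint", and that level would not be held. IAP 2.2 also keeps the sponsor blinded to any change of model after non-convergence. That is a sound integrity safeguard, and it means the rule has to be right beforehand.

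**Working it through.** **Reproducing the plan's own figures.** IAP 2.1 says "we plan to detect a 3-point difference on the primary efficacy endpoint", "assuming a common standard deviation of 9", with 85% power at two-sided 0.05.
- n per arm = 2 × (1.960 + 1.036)² × 9² / 3² = 161.6, so 162 per arm and 324 in total; 324 / 0.90 = 360. This agrees with the plan.
- O'Brien-Fleming-type spending at information fraction 0.5: 4 × [1 − Φ(2.241 / √0.5)] = 4 × [1 − Φ(3.170)] = 0.00305. With 0.003 spent at the interim, the final level is 0.0490. This also agrees.
- Evaluable at the interim: 180 × 0.90 = 162.

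**Simulation under no treatment effect.** From the documents: the planned model, three visits, about 50 sites, site-stratified blocked randomisation, 10% non-evaluable and the pooling algorithm of Protocol 9.4.1.1.2. Assumed, because the documents do not give them: block sizes 2 or 4, three enrolment spreads (equal, moderately uneven, very uneven), visit correlation 0.5-0.7, and 5% completely random dropout after each of the first two visits. There were 60,000 replicates per scenario. The ranges for the uncorrected sandwich cover normal, within-subject and between-subject reference degrees of freedom.

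| | Interim, 180 randomised | Final, 360 | Final, 540 |
|---|---|---|---|
| Pooled-site effects (very uneven, moderate, equal) | 31, 36, 42 | 38, 43, 49 | 42, 46, 50 |
| Sandwich SE / true SE | 0.915-0.945 | 0.954-0.969 | 0.969-0.978 |
| Nominal two-sided level | 0.003 | 0.049 | 0.049 |
| Actual level, uncorrected sandwich | 0.0044-0.0076 | 0.056-0.061 | 0.054-0.056 |
| Actual level, model-based SE with t | 0.0021-0.0028 | 0.048-0.050 | 0.048-0.049 |
| Actual level, Mancl-DeRouen sandwich with between-subject df | 0.0011-0.0014 | 0.038-0.041 | 0.041-0.043 |

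**Hand check.** If the standard error is r times the true value, the actual level is about 2 × [1 − Φ(r × z)].
- Interim, z = 2.968: r = 0.915 gives 2.715 and 0.0066; r = 0.945 gives 2.805 and 0.0050.
- 360, z = 1.969: r = 0.954 gives 1.878 and 0.060; r = 0.969 gives 1.908 and 0.056.
- 540: r = 0.969 gives 0.056; r = 0.978 gives 1.925 and 0.054.

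**Estimated rather than known covariance.** The table's runs took the working covariance as known. With heterogeneous Toeplitz estimated from the data (moderately uneven enrolment), the interim level was 0.0056 (between-subject t) to 0.0066 (normal) over 79,150 replicates. At 360 it was 0.060 to 0.061 over 40,290. With the sandwich at both looks and no sample-size increase, overall two-sided type I error was 0.062, against 0.050 with the true standard error.

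**Does a correction work?** In a further null simulation with an estimated Toeplitz covariance (about 35 pooled sites at the interim, 43 at 360), Kauermann-Carroll and model-based standard errors gave about 0.0024 at the interim and 0.048-0.050 at the final. The uncorrected sandwich gave about 0.005 and 0.060.

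**The case against.** The strongest objection is that the branch will almost never run. Three visits need six covariance parameters, with about 162 or more subjects to estimate them. In 400 simulated interim datasets the unstructured model converged every time. That check used an EM algorithm, which is more stable than the default in PROC MIXED, and simple rather than site-stratified randomisation, so it supports the point without proving it. If non-convergence happened 1% of the time (an assumption), overall type I error would be 0.050 + 0.01 × (0.062 − 0.050) = 0.0501. This stands: a reader might infer that the trial's main analysis or its unconditional type I error is materially inflated, and the documents do not support that.

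A false efficacy stop is also rarer than the rejection rates suggest. It needs the favourable direction and MADRS differences above 1.6 at Weeks 6, 8 and 10, and IAP 2.2 says stricter criteria are needed for an interim efficacy claim. Taking SE ratios of 0.92-0.93 at the interim, 0.95-0.957 at 360 and 0.97 at 540, the overall false-benefit rate is 0.0250-0.0259 if the futility rule is followed and 0.029-0.030 if it is not, against 0.025. Futility is a recommendation by the monitoring committee, so the first figures cannot be relied on.

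That the sandwich is uncorrected is an inference. The IAP's word empirical points that way; the SAP and Protocol say only sandwich. Yet a rule naming neither correction nor degrees of freedom allows the uncorrected version.

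Last, the sandwich was chosen to guard against a misspecified covariance, and purely model-based inference would give that up. The simulations hardly tested misspecification, and no results are available for the AR(1) or compound-symmetry fallbacks. This stands, and it is why the fix keeps a sandwich.

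**Conclusion.** The point holds as a defect in a prespecified fallback rule. Conditional on the fallback being used with an uncorrected sandwich, the standard error is about 5-9% too small at the interim and 3-5% at 360. The 0.003 test rejects at about 0.004-0.008, and the 0.049 test at about 0.056-0.061 at 360 or 0.054-0.056 at 540, all two-sided. The interim test statistic is inflated by about 6-9% (1/0.945 to 1/0.915), so conditional power would be affected too; that effect was not quantified.

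The sizes rest on assumed enrolment spread, block sizes and visit correlations. With about 31 site effects the interim rate can be as low as 0.0044.

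A reader might also infer that the fallback biases the treatment estimate itself when dropout depends on observed data and the covariance is wrong. Dropout was simulated as completely random, so this was not tested and forms no part of the conclusion.

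The trigger is improbable, the error in the primary test is material if it occurs, and the repair is small. It is worth making before the interim but does not undermine the main analysis.

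**What to change.** Make the same change in IAP 2.2, SAP 8.1.1.2 and Protocol 9.4.1.1.2:

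1. On non-convergence, first refit the same unstructured model with other starting values or a Cholesky parameterisation.
2. If a structured covariance is still needed, use a Kauermann-Carroll bias-corrected sandwich with stated between-subject degrees of freedom. The simulations used evaluable subjects minus pooled sites minus two, for example 162 − 36 − 2 = 124 at the interim. This keeps the protection against covariance misspecification that the plan wants.
3. Report model-based Kenward-Roger results alongside.
4. Rule out the uncorrected empirical estimator and name the correction exactly. The choice matters: Mancl-DeRouen was conservative (0.0011-0.0014 at the interim, 0.038-0.041 at 360).

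Write the fallback code into SAP 8.1.2 beside the existing unstructured call, so the independent analysis group has it before the interim. The cost is a sentence in each of the three documents, one extra code option, and a slightly larger standard error if the fallback is ever used.
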